6.5.3 Rescue Medicine

Not Applicable

6.5.4 Non-Research Standard of Care

Not Applicable

7. STUDY INTERVENTION DISCONTINUATION AND SUBJECT DISCONTINUATION/WITHDRAWAL

7.1 Halting Criteria and Discontinuation of Study Intervention

7.1.1 Individual Study Product Halting

Study product administration for any given subject may be stopped for SAEs, clinically significant adverse events, severe laboratory abnormalities, or any other medical conditions that indicate to the Investigator that continued dosing is not in the best interest of the patient.

In addition, a subject in this clinical study may discontinue study drug at their request for any reason. Every effort should be made to encourage subjects to remain in the study for the duration of their planned outcome assessments through Day 29. Subjects should be educated on the continued scientific importance of their data, even if they discontinue study drug.

Appendix C - ACTT-3: Remdesivir + Interferon Beta-1a

Unless the subject withdraws consent, those who discontinue study drug early will remain in the study and followed through Day 29. The reason for subject discontinuation of study drug(s) should be documented in the case report form.

7.1.1.1 Remdesivir Halting

See [Section 6.1.4.](#) for information about dosing modifications due to laboratory abnormalities.

For an individual subject, remdesivir infusions must be stopped if they have a suspected drug-related event of hypersensitivity (Grade 2 or higher) during or shortly after receiving the infusion. While there are no criteria for grading “hypersensitivity” in the Division of AIDS (DAIDS) Table for Grading the Severity of Adverse Events, sites should use acute allergic reaction from that toxicity table. Subjects who have the infusion stopped for a Grade 2 or higher allergic reaction that is temporally associated with the infusion and the PI believes it to be related to study product will not receive any more remdesivir.

7.1.1.2 Subcutaneous Interferon beta-1a and Placebo Injections Halting

See [Section 6.1.4.](#) for information about dosing modifications due to laboratory abnormalities.

The subject should not receive any additional subcutaneous injections for the remainder of the study if a subject develops any of the following conditions during the study:

- Disease progresses to the point that the subject requires high-flow oxygen or other non-invasive ventilatory support (i.e., a category 6 on ordinal scale) or mechanical ventilation or ECMO (category 7). Note: even if they improve to a category 4 or 5 before study Day 7, no additional subcutaneous injections will be given.
- Anaphylaxis temporally associated with subcutaneous injection
- Seizures not attributable to COVID-19, a medical complication of COVID-19 or another medical condition
- Thrombotic microangiopathy including thrombotic thrombocytopenic purpura and hemolytic uremic syndrome thought to be due to interferon beta-1a
- ALT or AST >8 times ULN
- Suspected drug-induced liver injury with symptomatic disease (i.e., jaundice, right upper quadrant pain or tenderness, fatigue, nausea, vomiting, etc.)

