Decreased peripheral blood counts have been described among those treated with interferon beta-1a including leukopenia, thrombocytopenia, neutropenia, lymphocytopenia, and anemia. We will mitigate the risk to the subject by limiting participation based on platelet count and WBC count at time of screening and actively monitoring the WBC count, differential, and hemoglobin. Subcutaneous injections will be held if the subject develops severe leukopenia and/or thrombocytopenia.

Cases of thrombotic microangiopathy (TMA) including thrombotic thrombocytopenic purpura (TTP) and hemolytic uremic syndrome have been reported with interferon beta products, including Rebif® (47). Some of these cases have been fatal. Cases have been reported several weeks to years after starting interferon beta. These adverse reactions have been identified during post-approval use of Rebif®. Because these events are passively reported from a population of uncertain size, it is not possible to reliably estimate their frequency or relationship to the drug. While the diagnosis of TMA may be difficult in hospitalized COVID-19 patients, safety laboratory monitoring will enable detection of the characteristic clinical features of TMA including thrombocytopenia, microangiopathic hemolytic anemia, and acute kidney injury. The principal treatment of drug-induced TMA is withdrawal of the suspected drug so subcutaneous injections will be discontinued if clinical signs and symptoms and laboratory findings consistent with TMA are detected. Cases will be managed as clinically indicated.

New or worsening autoimmune disorders have been described including systemic lupus

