Appendix C - ACTT-3: Remdesivir + Interferon Beta-1a

erythematosus and autoimmune hepatitis. These adverse reactions have been identified during post-approval use of Rebif®. Because these events are passively reported from a population of uncertain size, it is not possible to reliably estimate their frequency or relationship to the drug. As the risk of COVID-19 is likely larger than these risks, subjects with autoimmune disorders are permitted to participate in the study. All potential subjects will be informed of the risk for autoimmune diseases worsening or the development of a new autoimmune disorder at the time of informed consent.

Seizures have been temporally associated with interferon beta in clinical trials and post-marketing surveillance. It is not known if the events were related to multiple sclerosis, the active drug, or a combination of both. According to the package insert, a relationship between occurrence of seizures and the use of Rebif® has not been established. The subcutaneous injections (interferon beta-1a/placebo) will be discontinued if subject has a seizure that is not attributable to COVID-19, a medical complication associated with COVID-19, or other medical condition.

In clinical trials, the majority of subjects who received Rebif® had inflammation at the injection site. Other less common adverse reactions associated with subcutaneous interferon beta-1a included necrosis, atrophy, edema and hemorrhage at the injection site. During the study, we will alternate the injections site and monitor for signs of local reaction.

Rebif® contains albumin derived from human blood. Because of this, patients who have a history of hypersensitivity to human albumin will not be allowed to participate in the study. In addition, patients with a history of hypersensitivity to natural or recombinant interferon or any other component of the formulation will not be allowed to participate. Anaphylaxis is a rare complication and allergic reactions including skin rash and urticaria can also occur. If a subject develops anaphylaxis that is temporally related to subcutaneous injection, the injections will be discontinued.

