Appendix C - ACTT-3: Remdesivir + Interferon Beta-1a

The infusion should be held and not given if the subject is found to have any of the following laboratory values:

- eGFR decreases to < 20 mL/min
 - Remdesivir infusion will be held until the eGFR increases to a point that the potential benefit of giving remdesivir outweighs the potential risk. Note: this is consistent with the FDA Fact Sheet instructions for Health Care Providers, US EUA of Veklury® (remdesivir): "*Veklury is not recommended in adult patients with eGFR less than 30 mL/min...unless the potential benefit outweighs the potential risk*".
- ALT and/or AST increases to > 5 times upper limits of normal (ULN)
 - Remdesivir infusion will be held and not be restarted until the ALT and AST \leq 5 times ULN.

Interferon beta-1a /Subcutaneous Placebo component:

The subcutaneous injection should be held and not given if the subject is found to have any of the following laboratory values:

- ALT and/or AST increases to > 5 times ULN
 - Subcutaneous injection will be held and resume when ALT and AST \leq 5 times ULN.
- Total white cell blood cell count (WBC) <1000 cells/ μ L
 - Subcutaneous injection will be held and resume when WBC \geq 1000 cells/ μ L
- Platelet count <25,000/ μ L
 - Subcutaneous injection will be held and resume when platelet count \geq 25,000/ μ L.

Any dose that is held as described above, may be given later that day if the laboratory parameters improve. Any dose that is missed during the study due to any reason is not made up. The treatment course continues as described above even if the subject becomes PCR negative while hospitalized.

For laboratory values that meet permanent discontinuation thresholds (see [Section 7.1](#)), study product should be discontinued. However, if in the opinion of the investigator, the laboratory abnormality is due to intercurrent illness or another identified factor, laboratory tests may be repeated.

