6.3.2 Blinding and Masking Procedures

The subcutaneous interferon beta-1a/matching placebo component is blinded. Interferon beta-1a and placebo will be identical in appearance.

Unblinding of the study will occur after all subjects enrolled have reached the end of study, and these visits are monitored and data is cleaned, or if the DSMB recommends unblinding.

Treatment group-level unblinded analyses of subjects randomized in ordinal score category 6 may be conducted and published prior to the end of the trial to communicate the safety signal observed in this group by the DSMB during a safety review. If this analysis is conducted, only members of the unblinded analysis team will have access to subject-level treatment data while the study is ongoing; all other members of the study group will remain blinded to individual subject treatments as originally planned.

If AEs occur and investigators are concerned about the treatment allocation, the treatment can be discontinued. If a Serious Adverse Event occurs, that is thought to be related to the study drug, and the treating clinician believes that knowledge of the treatment arm may change the therapy provided to the patient, the individual subject can be unblinded. The procedure for unblinding will be further detailed in the Manual of Operations.

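### The required injection stop for thrombotic microangiopathy (Appendix C 7.1.1.2) is narrower than the stop the risk section (2.2.3.1) says will be applied

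*Protocol*

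**What the plan says.** Two current sections of Protocol Appendix C deal with stopping injections for TMA.

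- **2.2.3.1 (risks of interferon beta-1a)** notes that TMA has been reported with interferon beta products and that some cases were fatal. It describes the mitigation as "subcutaneous injections will be discontinued if clinical signs and symptoms and laboratory findings consistent with TMA are detected".
- **7.1.1.2 (halting of injections)** lists the conditions after which a subject should get no more injections for the rest of the study. The TMA item reads "Thrombotic microangiopathy including thrombotic thrombocytopenic purpura and hemolytic uremic syndrome thought to be due to interferon beta-1a".

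Three other provisions bear on the same subject:

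- 7.1.1 lets the investigator stop: product "may be stopped for SAEs, clinically significant adverse events, severe laboratory abnormalities" or other medical reasons.
- 6.3.2 is also permissive: "If AEs occur and investigators are concerned about the treatment allocation, the treatment can be discontinued".
- 6.1.4 holds the injection when platelets fall below 25,000/µL, but only for a time: "Subcutaneous injection will be held and resume when platelet count" is back at 25,000/µL or above.

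The SAP contains no TMA stopping rule.

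**The concern.** A halting list is what sites act on. If it is narrower than the mitigation in the risk section, the protection described there is not the one delivered. Here the difference is a causality judgement. The site must attribute the event to a named active drug while blinded to the injection, in patients in whom 2.2.3.1 itself accepts that TMA is hard to diagnose. The patient at risk is one with evolving TMA whose findings are put down to COVID-19 and who goes on receiving injections.

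What is at stake is individual safety, not the efficacy analysis or signal detection. Under 8.3.1, Grade 3 and 4 events are reported even when they may reflect COVID-19, and DSMB safety review (9.4.7.1) does not depend on this rule.

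**Working it through.** No sample size, power or error rate is involved. The check is a comparison of text plus a count of injections.

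**1. The two triggers.** 2.2.3.1 requires findings consistent with TMA, whatever the cause. 7.1.1.2 requires TMA and a judgement that interferon caused it. The second set lies inside the first. The cases left out are TMA findings attributed to COVID-19 or another cause.

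**2. Is this only a difference of style between the sections?** Compare each permanent stop described in 2.2.3.1 with its counterpart in 7.1.1.2:

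| Condition | 2.2.3.1 | 7.1.1.2 | Narrowed? |
|---|---|---|---|
| Seizure | Limited by cause | Same limit | No |
| Anaphylaxis | Temporal link to injection | Same | No |
| ALT/AST | >8 times ULN | >8 times ULN | No |
| Symptomatic drug-induced liver injury | Develops | Suspected | No; if anything wider |
| TMA | Consistent findings detected | Attributed to interferon | **Yes** |

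The seizure row is the informative one. Where the authors wanted a causal limit in 2.2.3.1 they wrote it: injections "will be discontinued if subject has a seizure that is not attributable to COVID-19, a medical complication associated with COVID-19, or other medical condition". The TMA sentence has no such limit.

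**3. Does any other rule require the stop?** Take a subject with falling hemoglobin, acute kidney injury and platelets of 30,000/µL, attributed by the site to COVID-19:

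- 2.2.3.1: stop.
- 7.1.1.2, TMA item: not met.
- 6.1.4: no injection hold, because 30,000 is above 25,000. There is no hemoglobin criterion, and the eGFR rule holds remdesivir only.
- 7.1.1 and 6.3.2: stopping is allowed but not required.

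**4. How many injections are at stake?** Four are planned, on Days 1, 3, 5 and 7. Injections at stake = 4 − doses already given.

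| TMA findings detected | Doses given | Injections at stake |
|---|---|---|
| Before the Day 3 dose | 1 | 4 − 1 = 3 |
| Before the Day 5 dose | 2 | 4 − 2 = 2 |
| Before the Day 7 dose | 3 | 4 − 3 = 1 |
| After the Day 7 dose | 4 | 4 − 4 = 0 |

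**5. When could findings appear?** Post-baseline safety draws are scheduled for Days 3, 5, 8 and 11, each ± 1 day. Only Days 3 and 5 fall before the last dose, plus the Day 8 draw if taken early, on Day 7 and before that day's injection. Of past TMA reports, 2.2.3.1 says: "Cases have been reported several weeks to years after starting interferon beta". Onset within the first week would therefore be unusual among reported cases.

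**The case against.** The best counter-argument reads the 2.2.3.1 sentence from its beginning: "The principal treatment of drug-induced TMA is withdrawal of the suspected drug so subcutaneous injections will be discontinued if" findings are detected. Its subject is drug-induced TMA and a suspected drug, so 7.1.1.2 could be seen as putting that suspicion into operation. It is possible that the authors meant only drug-related cases. But the opening clause gives the reason for stopping, and the condition that follows is detection of findings. If the narrower meaning was intended, 2.2.3.1 misstates the mitigation and the sections still disagree.

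Other points carry some weight:

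- Attribution conditions are common in this protocol. Drug-related hypersensitivity, drug-induced liver injury and seizures all have one. So such a condition is not out of place in itself; the point is that only TMA gains one between the two sections.
- Investigators judge relatedness while blinded for every reported event (8.3.4.2), so blinding adds only modestly to the concern.
- Existing protection is wider than the platelet hold alone suggests. Missed doses are not made up, so a platelet count that stays low withholds the remaining injections. Progression to ordinal category 6 or 7 ends injections whatever the cause. Section 6.1.4 also uses routine-care laboratory results, so findings may surface between scheduled draws.
- Thrombocytopenia can occur in COVID-19 (noted in Appendix B 2.2.3.1), so a findings-based rule would stop injections in some subjects whose findings are disease-driven. The documents give no basis for saying how many.

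These points reduce the size of the problem. None creates a required stop for the omitted cases.

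**Conclusion.** The concern holds. As written, the rule sites must follow is weaker than the mitigation the protocol describes for a reaction with reported fatal cases, and the gap is left to investigator discretion. The consequence is small: at most three injections per affected subject, in an event whose frequency the protocol says cannot be reliably estimated, with no effect on adverse event capture, DSMB review or any endpoint definition. It should still be corrected, because it is a contradiction within a safety rule and is easily removed.

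The conclusion rests on two readings: that the 7.1.1.2 list works as the required-stop list although its verb is should, and that the trigger in 2.2.3.1 is detection of findings, as its wording states.

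**What to change.** In Appendix C 7.1.1.2, delete the clause that ties TMA to interferon and base the bullet on findings, for example: *clinical and laboratory picture consistent with thrombotic microangiopathy (TTP and HUS included), regardless of presumed cause*. Using suspected TMA as the trigger in both sections would also remove the mismatch, provided that suspicion does not require attribution to interferon. Narrowing 2.2.3.1 instead would make the texts agree but give up the stated protection.

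The cost is one line of protocol wording and a notice to sites. Subjects in either arm who meet the wider trigger, including some whose findings are driven by COVID-19, would lose their remaining injections, at most three each. They would stay in follow-up through Day 29, as 7.1.1 already provides for subjects who discontinue study drug.

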7.1.2 Study Halting

Given the potential severity of COVID-19, there are no pre-specified study stopping rules. Instead there will be close oversight by the protocol team and frequent DSMB reviews of the safety data.

7.2 Withdrawal from the Study

Subjects are free to withdraw from participation in the study at any time upon request, without any consequence. Subjects should be listed as having withdrawn consent only when they no

Appendix C - ACTT-3: Remdesivir + Interferon Beta-1a

longer wish to participate in the study and no longer authorize the Investigators to make efforts to continue to obtain their outcome data or safety assessment.

The investigator may also withdraw a subject from the study. However, the investigator will be encouraged to allow subjects to remain in the study to be followed for safety and final outcome assessment at Day 29 (i.e., the ordinal scale and mortality) even if they decide to discontinue study products and research laboratory draws. Withdrawing a subject from the study due to an inability to contact them for the Day 15 and/or Day 22 follow-up visit is discouraged given the possibility of readmission and chaotic social circumstances resulting from the pandemic.

Subjects who withdraw from this study or are lost to follow-up after signing the informed consent form (ICF) and administration of the study product, will not be replaced. The reason for subject withdrawal from the study will be recorded on the appropriate CRF.

7.3 Lost to Follow-Up

A subject will be considered lost to follow-up if the site is unable to contact him or her by phone or other means such as text, email, fax or letter (as approved by the IRB) for all follow-up assessments at Day 15, 22 and 29. In lost to follow-up cases, attempts to contact the subject should be made and these efforts should be documented in the subject's records.

7.4 Readmission

If a subject is discharged from the hospital and then readmitted prior to Day 11, they may be given the remainder of the remdesivir infusions and if prior to Day 8, they may be given the remainder of the subcutaneous injections. If the subject did not withdraw his/her consent to participate in the study, there is no need to reconsent upon readmission to the study hospital. However, the site will need to inform them that since he/she was readmitted, study product administration will resume and confirm that they still agree to receive study product.

The natural history of COVID-19 and its impact on pre-existing medical conditions is not completely understood. Because of this, all readmissions, regardless of reason, should be documented and the subject should get daily clinical status assessments (i.e., ordinal scale and NEWS) and other procedures done as per the SOA upon readmission. If the subject is re-admitted with diminished mental capacity, the site should discuss continued study participation with a LAR.

The study team will need to notify the study pharmacist of the readmission. The subject will not get the doses that they missed after being discharged. Upon readmission, the subject will get maintenance doses of infusion only since they already received the loading dose of the study product infusion on Day 1. No study product infusions should be given past Day 10. No subcutaneous injection should be given past Day 7. For all data collection procedures required for those readmitted, please see the MOP.

8. STUDY ASSESSMENTS AND PROCEDURES

8.1 Screening and Efficacy Assessments

8.1.1 Screening Procedures

Screening procedures may be done over one to two calendar days (from Day -1 to Day 1). However, in many cases all the screening assessments can be done in less than 24 hours. If that is the case, Day 1 pre-study product administration baseline assessments, specimen collection and the initial study product administration can occur on the same calendar day as the screening procedures.

After the informed consent, the following assessments are performed to determine eligibility:

- Confirm the positive SARS-CoV-2 test result (per inclusion criteria).
- Take a focused medical history, including the following information:
 - Day of onset of COVID-19 signs and symptoms.
 - History of chronic medical conditions, including chronic liver disease and chronic oxygen requirement. This includes use of continuous positive airway pressure (CPAP) ventilatory support at night and oxygen by nasal cannula at home or nursing home prior to onset of COVID-19. See conditions included on the Medical History (CMX) data collection form.
 - History of medication allergies including history of hypersensitivity to natural or recombinant interferon, human albumin, or any other component of the interferon beta-1a formulation.
 - Medications and therapies for this current illness taken in the 7 days prior to Day 1, and history of any medication listed in the exclusion criteria.
 - Ask if they are participating in another clinical trial or plan to enroll in another clinical trial in the next 28 days.
- Women of childbearing potential should be counseled to either practice abstinence or use at least one primary form of contraception not including hormonal contraception from the time of screening through Day 29. Women should be confirmed to not be breastfeeding.
 - Note: If a woman is either postmenopausal (i.e., has had ≥ 12 months of spontaneous amenorrhea) or surgically sterile (i.e., has had a hysterectomy, bilateral ovariectomy (oophorectomy), or bilateral tubal ligation), she is not considered to be of childbearing potential.
- Height and weight (height can be self-reported).
- Results of recent radiographic imaging (x-ray or CT scan).
- SpO₂.
- Blood for screening laboratory evaluations if not done as part of routine clinical care in the preceding 48 hours:
 - ALT and AST
 - Assess if ALT or AST > 5 times ULN
 - WBC

- Assess if WBC <1500 cells/ μ L
- Platelet count
 - Assess if platelet count <50,000/ μ L
- Creatinine (and calculate eGFR).
 - Any automated calculation by the clinical laboratory or published formula for the calculation of eGFR is acceptable. The site should select a formula to be used for all subjects enrolled at the site for the duration of the study.
- Urine or serum pregnancy test (in women of childbearing potential). See instructions below for women who are less than 6 weeks postpartum:
 - Do not do a pregnancy test if the patient is post-partum and has not left the hospital since delivery. The pregnancy test will likely give a false-positive result as serum human chorionic gonadotropin (hCG) is usually detected for up to 4 to 6 weeks after delivery.
 - For women who are less than 6 weeks postpartum and have left the hospital, any positive pregnancy test should be repeated to determine if the HCG is declining as predicted after delivery and therefore the result is a false-positive. Of note, women who are less than 6 weeks postpartum and have had heterosexual intercourse since delivery and hospital discharge are unlikely to be pregnant because the average time to first ovulation varies from 45 to 94 days postpartum, with the earliest reported ovulations at 25 and 27 days postpartum.

Clinical screening laboratory evaluations will be performed locally by the site laboratory. The volume of venous blood to be collected is presented in [Table 3](#). A screening lab (i.e., from the hematology and chemistry laboratory panels) may be repeated once if, in the opinion of the investigator, the laboratory abnormality is due to an intercurrent transient condition or it is an aberrant laboratory value.

The overall eligibility of the subject to participate in the study will be assessed once all screening values are available. The screening process can be suspended prior to complete assessment at any time if exclusions are identified by the study team.

Study subjects who qualify will be randomized in the Advantage eClinical system, and all others will be registered as screen failures. The ordinal scale and the NEWS should be done at the time of randomization; the site will need this data to randomize the subject in eClinical. The study team has 24 hours to complete other Day 1 baseline assessments prior to the first study product administration including the collection of OP swab and blood and completing or recording a baseline physical examination that was done. Clinical laboratory tests collected as part of routine care of the patients in the 36 hours prior to first dose qualify for baseline safety tests on Day1.

